7.3.14. Time to first nasal surgery or course of systemic steroids

The time to first nasal surgery or course of systemic steroids for nasal polyps will be determined as the number of days from the date of first dose of study medication to the date of first nasal surgery or course of systemic steroids for nasal polyps (see Section 14.6.5). If a participant withdraws from the study before experiencing nasal surgery or having a course of systemic steroids for nasal polyps, the event time will be censored at the time of study withdrawal.

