7.3.14.1. Summary Measure

The summary measure of treatment effect will be the hazard ratio, the ratio of hazards corresponding to treatment with mepolizumab compared with placebo. For this endpoint the hazard represents the probability of nasal surgery or course of systemic steroids for nasal polyps for a participant at a given point in time following first dose of interventional product, given the participant has not experienced either event prior to that time.

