7.3.14.4. Statistical Analyses / Methods

Endpoint / Variables					

 Time to first nasal surgery or course of systemic steroids for nasal polyps 					
Model Specification					

 Cox proportional hazards model with covariates as follows: 
 
 Fixed Categorical:	Treatment group, Region	
 
 Fixed Continuous:	Baseline total nasal polyps endoscopic score (centrally read data), Baseline nasal obstruction VAS, Log_e baseline blood eosinophil count, Number of previous surgeries (1, 2, >2; ordinal)	
 
 
 Participants with missing covariate information will be excluded from the analysis 		Fixed Categorical:	Treatment group, Region	Fixed Continuous:	Baseline total nasal polyps endoscopic score (centrally read data), Baseline nasal obstruction VAS, Log _e baseline blood eosinophil count, Number of previous surgeries (1, 2, >2; ordinal)
Fixed Categorical:	Treatment group, Region				
Fixed Continuous:	Baseline total nasal polyps endoscopic score (centrally read data), Baseline nasal obstruction VAS, Log _e baseline blood eosinophil count, Number of previous surgeries (1, 2, >2; ordinal)				
Model Checking & Diagnostics					

 A log(-log(survival)) plot by treatment group will be used to assess the assumption of proportional hazards. 					
Model Results Presentation					

 The number of participants with an event, the number censored due to study withdrawal and at study completion will be presented by treatment arm. The hazard ratio with corresponding 95% CI and p-value from the Cox proportional hazards model will be presented. A summary and graph of the Kaplan-Meier estimate of the cumulative proportion of participants with nasal surgery within each treatment arm over time will be produced. 					
Subgroup Analyses					

 No subgroup analyses are planned for this endpoint. 					
Sensitivity and Supportive Analyses					

 No sensitivity/supportive analyses are planned for this endpoint. 					

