
 The total number of mgs of prednisolone equivalent OCS use per year will be calculated as follows and will be based on systemic steroids taken via the following routes: Oral, Intravenous, Intramuscular: $\left(\frac{\text{Total cumulative mgs prednisolone – equivalent OCS use in period}}{\text{Total number of days in period}} \right) * 365.25$ 
 The following table from the study reference manual will be used for conversion of intravenous and oral steroid use into prednisolone equivalent OCS use in mgs:

Systemic steroid use	
Glucocorticoid	Approximate equivalent dose (mg)
Short-Acting	
Cortisone	25
Hydrocortisone	20
Intermediate-Acting	
Methylprednisolone	4
Prednisolone	5
Prednisone	5
Triamcinolone	4
Long- Acting	
Betamethasone	0.6-0.75
Dexamethasone	0.75

- Participants who withdraw early from the study will have yearly use estimated based on use during the study.

Courses of Therapy

- A course of systemic steroid therapy is defined by the start and stop date of therapy.
- If the start date of a course of systemic steroid therapy occurs <7 days from the stop date of the previous course, it will be considered a continuation of the same course.

Days on Therapy

- The duration of a course of systemic steroids will be calculated as the number of days between the start and stop date of the course: stop date – start date + 1
- For each participant the total number of days on systemic steroids will be calculated as the sum of the duration of each of their courses of therapy.
- For each participant the percentage of days on systemic steroids will be calculated as follows:

$$\left(\frac{\text{Total number of days on systemic steroids}}{\text{Total number of days in the study}} \right) * 100$$

Nasal Surgery or Course of Systemic Steroids

Time to first nasal surgery or course of systemic steroids

- Calculated as (Date of first nasal surgery/course of systemic steroids – Date of first dose of study treatment) + 1
- Analysis excluding data reported in the follow-up period after Week 52:
For participants who withdraw from the study before Week 52 and before experiencing either event, event times will be censored at the time of study withdrawal
For participants who complete to Week 52 without experiencing either event, event times will be censored at the time of the Week 52 visit

Antibiotic Use
Courses of Therapy

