2.51.	ITT	SHELL	Summary of Peak Nasal Inspiratory Flow (PNIF)	Include actual and change from baseline Footnote: Includes data reported up to Week 52 Programming Note: summaries from dataset with assigned values for subjects with surgery/missing data	SAC [2]
2.52.	ITT	SHELL	Summary of Total Prednisolone-equivalent OCS Use for Nasal Polyps (mgs per year)	Footnote: Includes data reported up to Week 52	SAC [2]
2.53.	ITT	SHELL	Summary of Days on Systemic Steroids for Nasal Polyps	Footnote: Includes data reported up to Week 52 Include days on therapy and percentage of days on therapy	SAC [2]
2.54.	ITT	SHELL	Time to First Course of Systemic Steroids for Nasal Polyps	Footnote: Includes data reported up to Week 52	SAC [2]
2.55.	ITT	SHELL	Analysis of Time to First Nasal Surgery or Course of Systemic Steroids for Nasal Polyps	Footnote: Includes data reported up to Week 52	SAC [2]
2.56.	ITT	SHELL	Summary of Number of Courses of Antibiotics	Footnote: Includes data reported up to Week 52 Footnote: Courses of antibiotics separated by <7 days are considered a continuation of the same course Include n (%) with 0 vs ≥ 1 and 0, 1, 2, courses and total number of courses	SAC [2]
2.57.	ITT	SHELL	Summary of On-Treatment Blood Eosinophils (GI/L)	Include absolute and ratio to baseline values	SAC [2]

CONFIDENTIAL

205687

Efficacy: Tables					
No.	Population	IDSL / Example Shell	Title	Programming Notes	Deliverable [Priority]
2.58.	ITT	SHELL	Analysis of On-Treatment Blood Eosinophils (GI/L) Ratio Compared to Baseline Mixed Model Repeated Measures		SAC [2]
Other Endpoints – Health Economics/Medical Resource Utilisation					
2.59.	ITT	SHELL	Summary of SF-36 Domain Scores and Component Summary Scores	
Include 8 domain scores bodily pain, general health, mental health, physical functioning, role emotional, role physical, social functioning and vitality and Mental and Physical Component Summary scores.
 
Include actual and change from baseline (b) (4)
 
Footnote: Includes data reported up to Week 52
 
Programming Note: summaries from dataset with assigned values for subjects with surgery/missing data
	SAC [2]
2.60.	ITT	SHELL	Summary of Work Productivity and Activity Impairment Questionnaire (WPAI)	
Footnote: Includes data reported up to Week 52
 
Include only summary variables
	SAC [2]
Other Endpoints – Participants with Asthma					

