Efficacy: Figures					
No.	Population	IDSL / Example Shell	Title	Programming Notes	Deliverable [Priority]
2.13.	ITT	SHELL	Figure of Median Change from Baseline Composite VAS Score - Nasal Symptoms in each 4-Weekly Period	Median and 95%CI Footnote: Includes data reported up to Week 52	SAC [1]
2.14.	ITT	SHELL	Figure of Median Change from Baseline Loss of Smell VAS Score in each 4-Weekly Period	Median and 95%CI Footnote: Includes data reported up to Week 52	SAC [1]
Other Endpoints					
2.15.	ITT	SHELL	Figure of Total Endoscopic Nasal Polyps Score (Centrally Read) Responders by Visit	OR and 95%CI Footnote: Includes data reported up to Week 52	SAC [2]
2.16.	ITT	SHELL	Figure of University of Pennsylvania Smell Identification Test (UPSIT) Change from Baseline by Visit	Median and 95%CI Footnote: Includes data reported up to Week 52	SAC [2]
2.17.	ITT	SHELL	Figure of SNOT-22 Responders by Visit	OR and 95%CI Footnote: Includes data reported up to Week 52	SAC [2]
2.18.	ITT	SHELL	Kaplan-Meier Time to First Inclusion on Waiting List for Nasal Polyps Surgery	Footnote: Includes data reported up to Week 52	SAC [2]
2.19.	ITT	SHELL	Kaplan-Meier Time to First Course of Systemic Steroids	Footnote: Includes data reported up to Week 52	SAC [2]
2.20.	ITT	SHELL	Kaplan-Meier Time to First Nasal Surgery or Course of Systemic Steroids	Footnote: Includes data reported up to Week 52	SAC [2]
2.21.	ITT	SHELL	Figure of On-Treatment Blood Eosinophils Absolute Values	No reference line. Include screening/baseline geometric mean values without 95% CI. Week 4 onwards adjusted estimates from MMRM model with 95% CI.	SAC [2]

CONFIDENTIAL

205687

Efficacy: Figures					
No.	Population	IDSL / Example Shell	Title	Programming Notes	Deliverable [Priority]
2.22.	ITT	SHELL	Figure of On-Treatment Blood Eosinophils Ratio to Baseline	Reference line at 1	SAC [2]
Other Endpoints – Maintenance of Response Following Cessation of Interventional Product (Follow-Up Period After Week 52)					
2.23.	FU	SHELL	Kaplan-Meier Time to First Nasal Surgery for Subjects in the Follow-Up Period After Week 52		SAC [2]
2.24.	FU	SHELL	Kaplan-Meier Time to First Inclusion on Waiting List for Nasal Polyps Surgery for Subjects in the Follow-Up Period After Week 52		SAC [2]
2.25.	FU	SHELL	Figure of Blood Eosinophils for Subjects in the Follow-Up Period After Week 52		SAC [2]

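### The derivation and the Kaplan-Meier specification for time to first nasal surgery or nasal-polyp steroid course do not match the event that SAP Section 7.3.14 defines

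*SAP*

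**What the plan says.** All the wording below is in the current SAP (Amendment 1), not the superseded version reproduced after it.

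Section 7.3.14 runs the clock from first dose to the "date of first nasal surgery or course of systemic steroids for nasal polyps (see Section 14.6.5"). The summary measure in 7.3.14.1 agrees: "the hazard represents the probability of nasal surgery or course of systemic steroids for nasal polyps for a participant at a given point in time". So does the endpoint line for the Cox model in 7.3.14.4, "Time to first nasal surgery or course of systemic steroids for nasal polyps", and so does Table 2.55, "Analysis of Time to First Nasal Surgery or Course of Systemic Steroids for Nasal Polyps".

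The derivation in 14.6.5 takes the "Date of first nasal surgery/course of systemic steroids" minus the date of first dose, plus one, and names no indication. The same section identifies a course by its start and stop dates and joins courses less than 7 days apart, again without using the indication. The Kaplan-Meier figure for this endpoint, Figure 2.20, is titled "Kaplan-Meier Time to First Nasal Surgery or Course of Systemic Steroids".

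Under results presentation, 7.3.14.4 asks for "A summary and graph of the Kaplan-Meier estimate of the cumulative proportion of participants with nasal surgery within each treatment arm". The corresponding bullet for the key secondary endpoint, time to first nasal surgery (SAP 7.2.1.4), has the same wording.

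**The concern.** Section 7.3.14 sends the programmer to 14.6.5 for the event date, and the rule found there drops the restriction that 7.3.14 imposes. This can change who has an event, because systemic steroids are also given for asthma in this trial. SAP 14.6.5 defines a clinically significant asthma exacerbation partly by systemic steroid use, and SAP 7.4 analyses participants with asthma separately. A participant whose only course was for asthma is censored under 7.3.14 and has an event under a literal reading of 14.6.5. Protocol 3.2.3 reports that mepolizumab reduces asthma exacerbations, so such courses might not be balanced between arms. The result carries a hazard ratio, confidence interval and p-value.

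The Kaplan-Meier bullet raises a separate problem. Followed as written, it would plot surgery alone beside a Cox model of the composite, and the curve and the hazard ratio would then describe different events.

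The composite is not among the endpoints in Protocol Section 4 or SAP 2.1, so these SAP passages are its only definition.

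**Working it through.** The plan states no event rate, sample size or power for this composite, so there is no figure to reproduce. The check is a comparison of text, followed by two illustrations.

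**Step 1. The wordings side by side.**

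| Place in the current SAP | Surgery counts | Steroid course counts |
|---|---|---|
| 7.3.14 text, 7.3.14.1, Cox endpoint line in 7.3.14.4, Table 2.55 | yes | if for nasal polyps |
| 14.6.5 derivation, Figure 2.20 title | yes | no indication named |
| 7.3.14.4 Kaplan-Meier bullet | yes | not mentioned |

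Rows 1 and 2 differ for participants whose first or only course was for another indication. Rows 1 and 3 differ for every participant with a nasal-polyp course and no surgery, and in event time for anyone whose course came before surgery.

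**Step 2. Participants missing from a surgery-only curve.** Inputs: 200 per arm, with surgery in 40% on placebo and 25% on mepolizumab (Protocol 10.1). Assumption: a fraction f of those without surgery have a nasal-polyp steroid course, with the same f in both arms.

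- Surgery events: 200 × 0.40 + 200 × 0.25 = 80 + 50 = 130.
- No surgery: 120 + 150 = 270.
- Steroid-only events, 270 × f: 27 at f = 10% and 108 at f = 40%.
- Composite total: 157 to 238, against 130 on the curve.

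**Step 3. Effect of admitting asthma-only courses.** Every rate here is assumed. The nasal-polyp composite is set at 60% on placebo and 42% on mepolizumab by Week 52. Hazards are taken as exponential and asthma-only courses as independent of the composite.

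- Hazard: h = −ln(1 − p). Placebo: −ln 0.40 = 0.916. Mepolizumab: −ln 0.58 = 0.545. HR = 0.545 / 0.916 = 0.59.
- With asthma hazards a added: HR = (0.545 + a for mepolizumab) / (0.916 + a for placebo).
- Extra participants with an event per arm = 200 × (1 − nasal-polyp rate) × asthma-only rate, that is 80 × rate on placebo and 116 × rate on mepolizumab.

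| Asthma-only rate, placebo / mepolizumab | HR | Extra, placebo | Extra, mepolizumab |
|---|---|---|---|
| 10% / 10% | (0.545 + 0.105) / (0.916 + 0.105) = 0.64 | 8 | 11.6 |
| 15% / 8% | (0.545 + 0.083) / (0.916 + 0.163) = 0.58 | 12 | 9.3 |
| 25% / 13% | (0.545 + 0.139) / (0.916 + 0.288) = 0.57 | 20 | 15.1 |

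The direction is not fixed. Balanced asthma courses dilute the effect, and courses that mepolizumab reduces enlarge it slightly. The largest movement of the three is towards no effect.

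The assumed 60% and 42% are compatible with Step 2. They imply 200 × (0.60 − 0.40) + 200 × (0.42 − 0.25) = 40 + 34 = 74 steroid-only events, inside the range 27 to 108.

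**The case against.** The strongest reply is that the event is not in doubt. Every passage that sets out the endpoint says the same thing, and SAP 5.4.1 names Section 7 as the place where the analysis methods are given in full. On that view 14.6.5 supplies only date arithmetic, and the indication comes from Section 7.

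The SAP's habits support this. The heading of 7.3.14 drops the qualifier that its own text contains. The heading of 7.3.12.3 and Figure 2.19 also drop it, although the text of 7.3.12.3 and Table 2.54 limit that analysis to nasal polyps. The dose and days-on-therapy rules in 14.6.5 are equally unqualified, yet they serve analyses that 7.3.12.1 and 7.3.12.2 restrict to nasal polyps. As for the Kaplan-Meier bullet, the display list already has a surgery-only curve (Figure 2.8), and the title of Figure 2.20 names the composite.

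Most of this stands. A reader might infer that the SAP holds three competing definitions of the event. It does not: Section 7 is consistent, the unrestricted version rests on an absent qualifier, and the surgery-only version is one reporting bullet that appears to be carried over from 7.2.1.4. A reader might also infer that asthma courses will be counted, or that the hazard ratio is biased in favour of mepolizumab. No passage says that courses for other indications count, and the documents give no rates from which to claim a direction.

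The reply does not remove the mismatch. Section 7.3.14 refers explicitly to 14.6.5, and a derivation is what gets programmed. The Kaplan-Meier bullet is itself part of Section 7, so giving Section 7 precedence does not correct it.

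**Conclusion.** The point holds as a mismatch between a consistently defined event and two places that carry it out: the 14.6.5 derivation (with the Figure 2.20 title) and the Kaplan-Meier bullet in 7.3.14.4. The best-supported reading is first nasal surgery or first systemic steroid course for nasal polyps.

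The larger discrepancy is in the curve. Read literally, it would omit 27 to 108 of 157 to 238 participants with an event, on the planning surgery rates and an assumed 10% to 40% steroid use among those without surgery. The effect on the Cox result is modest: from 0.59 to between 0.57 and 0.64, with 8 to 20 extra events per arm. That rests wholly on assumed rates, so it shows sensitivity and is not an estimate of bias.

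The consequence is minor. This is one of the other efficacy analyses in SAP 7.3. It is absent from the hierarchy in SAP 5.5, and its outputs are not in the headline delivery. The co-primary and secondary tests, alpha and sample size do not change.

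**What to change.** Make three wording edits before the randomisation codes are released:

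1. In SAP 14.6.5, define the event date as the earlier of first nasal surgery and first course of systemic steroids for nasal polyps.
2. In the Kaplan-Meier bullet of 7.3.14.4, replace *with nasal surgery* by *with nasal surgery or a course of systemic steroids for nasal polyps*.
3. Retitle Figure 2.20 to match Table 2.55.

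It would also help to add one sentence to 14.6.5 on how a course is attributed to nasal polyps, including when courses less than 7 days apart are joined and their recorded reasons differ.

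No new data are needed, because Protocol 7.6 already requires the reason for use of each medication to be recorded. The cost is a short SAP revision and a check that the table and figure programs use the same event variable.

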14.6.6. Safety**Adverse Events****Drug Related AE's**

- AEs where the response to "Is there a reasonable possibility that the AE may have been caused by the Study Treatment?" is "Yes" or it is missing

AE's Leading to Permanent Discontinuation of Study Treatment or Withdrawal from Study

- AE's leading to permanent discontinuation of study treatment are defined as AEs where the response to "Most Clinically Significant Action Taken with Study Treatment(s) as a Result of the AE" is "Study Treatment(s) Withdrawn".
- AEs leading to withdrawal from study are defined as AEs where the response to "Did the subject withdraw from study as a result of this AE?" is "Yes".

AE's on Day of Dosing

 These are defined as AEs with an onset date on the same day as dosing with interventional product and an onset time on or after the time of dosing with interventional product on the given day.
AE Time Since First Dose

 If AE onset time is missing, calculate in days as follows: 
 If AE start date < Date of first dose of Interventional Product, then Time since first dose = AE start date - Date of first dose of Interventional Product If AE start date ≥ Date of first dose of Interventional Product, then Time since first dose = AE start date – Date of first dose of Interventional Product +1 If AE start date or date of first dose of Interventional Product is missing time since first dose is missing. If AE onset time is present, calculate as above but in days, hours, minutes using AE start date/time and date/time of first dose of interventional product
AE Duration in Days

 If AE onset time is missing calculate in days: AE end date - AE start date + 1 If AE onset time is present calculate in days, hours, minutes as above but using AE end date/time and AE start date/time. If AE start/end date is missing duration is missing.
AE's of Special Interest

 Section 8.2 provides a full list of AEs of special interest for this compound. AESIs of anaphylaxis reactions, systemic reactions, and local injection site reactions are collected via targeted eCRF. The AESIs of potential opportunistic infections, malignancies, serious CVT events and serious ischemic events will be identified from a list of relevant preferred terms maintained within a project level reference dataset; created based on the latest version of the MedDRA dictionary available at the time of database freeze for this study (See Program Safety Analysis Plan for additional details).

ECG						
Multiple Assessments						

 Where multiple assessments are performed at a given time point, the mean value over the replicate assessments will be used for summary statistics; the highest value amongst the individual replicate assessments will be used in the evaluation of the highest post-baseline value. 						
QTc values						

 A single 12-lead ECG machine will be used to assess heart rate and measure PR, QRS, QT and QTc intervals QTc(F) will be derived from QT (uncorrected) and RR interval as: $QTc(F) = \frac{QT}{\sqrt[3]{RR/1000}}$ QTc(B) will be derived from QT (uncorrected) and RR interval as: $QTc(B) = \frac{QT}{\sqrt{RR/1000}}$ If present the reported QTc value will be included in any summaries, else the derived QTc value will be included. 						
Categorised QTc values						
Individual maximum QTc(F) and QTc(B) values and maximum change from baseline QTc(F) and QTc(B) will be categorised as follows:						

 
 	Lower	Upper	
 
 QTc Interval (msec)		≤ 450	
 
		Lower	Upper	QTc Interval (msec)		≤ 450
	Lower	Upper				
QTc Interval (msec)		≤ 450				

CONFIDENTIAL

2020N427698_00

205687

		> 450	≤ 480	
		> 480	≤ 500	
		> 500		
	QTc Change from Baseline (msec)		≤ 30	
		> 30	≤ 60	
		> 60		

Laboratory Parameters**Character Values**

- If a laboratory value which is expected to have a numeric value for summary purposes has a non-detectable level reported in the database, where the numeric value is missing, but instead a character value starting with '<x' or '>x' (or indicated as less than x or greater than x in the comment field) is present, a numeric value will be imputed; the number of significant digits in the observed value will be used to determine how much to add or subtract to impute the corresponding numeric value:
 - Example 1: 2 Significant Digits = '< x' imputed as $x - 0.01$
 - Example 2: 1 Significant Digit = '> x' imputed as $x + 0.1$
 - Example 3: 0 Significant Digits = '< x' imputed as $x - 1$
- Laboratory values with missing values due to being below the limit of quantification (BLQ) for that parameter will have a value imputed as half the lower limit of quantification for that measure (i.e. the lowest observed value for that measure within the entire study database).
- Values of potential clinical concern and those outside the ≥ 2 , ≥ 3 etc. limit of normal will be identified as detailed in Section 14.8.

Blood Eosinophils

- Blood eosinophil counts will be log transformed (\log_e) prior to analysis. The log transformation for values of 0GI/L will be based on a value of 0.005GI/L.

Biomarkers

- No analyses of additional biomarker will be carried out as part of this RAP.

14.7. Appendix 7: Reporting Standards for Missing Data

14.7.1. Premature Withdrawals

Element	Reporting Detail
General	
 • The protocol objective is to collect data over the full study treatment period (up to Week 52) for all participants, whether they continue on interventional product (IP) and complete Week 52 on-treatment, or whether they withdraw prematurely from IP. 
 ○ For the participants who withdraw prematurely from IP before Week 52 and agree to the continued collection of data off-treatment, data will be collected for up to 52 weeks after randomization (or up to 76 weeks if the participant enters the Follow-up period after Week 52) either through clinic visits or via phone contact, in accordance with the participants existing visit schedule. ○ Where available, off-treatment data will be included in the analysis of the co-primary endpoints and, unless otherwise indicated, in the analysis of other efficacy endpoints. • A participant will be considered to have completed study treatment if he/she continues to take study treatment until Visit 14 (Week 48) and completes Visit 15 (week 52). • As specified in the protocol participants will be considered to have completed the study upon completion of Visit 15 (Week 52) regardless of whether they continue to take IP. • A participant eligible for the no-treatment follow-up will be considered to have completed follow-up if they continue to participate in the study until Visit 18 (Week 76) • All available data from participants who were withdrawn from the study will be listed and all available planned data will be included in summary tables and figures, unless otherwise specified. • Withdrawal visits will be slotted as per Appendix 3: Assessment Windows or will be summarised as withdrawal visits.
Pre-Screen/Screen and Run-in Failures	
 • Participants are assigned a subject number at the time of signing informed consent. • Pre-Screen Failure: A participant who is assigned a subject number but did not continue through to Visit 1. • Screening Failure: Participant performs a Visit 1 procedure, but does not enter the run-in period • Run-in Failure: Participant enters the run-in period, may perform a Visit 2 procedure, but is not subsequently randomised.

